10.2 SECONDARY EFFICACY PARAMETER

None.

10.3 ADDITIONAL EFFICACY PARAMETERS

The overall relapse rate, as well as the relapse rates for sub-categories of interest including modified manic episode and modified depressive episode will be presented.

Time to early discontinuation with any reason (including relapse) during the DBTP for the DB ITT population will be analyzed using the same method used to analyze the primary efficacy variable.

For the following continuous efficacy variables, the change from baseline refers to the change from OL baseline during the OLTP, and the change from DB baseline during the DBTP, unless stated otherwise.

For Open-label Treatment Period

- Change from baseline in YMRS total score by visit
- Change from baseline in MADRS total scores by visit
- Change from baseline in CGI-S score by visit
- CGI-I score by visit
- Change from baseline in PSP total score and sub-domain score by visit

For Double-blind Treatment Period

- Change from DB baseline in YMRS total score by visit
- Change from DB baseline in MADRS total score by visit
- Change from DB baseline in CGI-S score by visit
- CGI-I score by visit
- Change from DB baseline in PSP total score and sub-domain score by visit

Descriptive statistics (n, mean, standard deviation, median, Q1, Q3, minimum and maximum) for additional efficacy parameters will be provided by visit for the OL ITT population and the DB ITT population using both last-observation-carried forward (LOCF) and observed cased (OC) approaches. LOCF approach will be used to impute missing postbaseline values. Imputation of missing values will be done for the OLTP and the DBTP separately.

For the DBTP, the additional efficacy parameters will be analyzed by using a mixed-effects model for repeated measures (MMRM) with treatment group, region (US and non-US), modified index episode strata (manic or depressive), visit, and treatment group-by-visit interaction as fixed effects and the baseline value and baseline-by-visit interaction as the covariates. An unstructured covariance matrix will be used. The Kenward-Roger approximation ([Kenward and Roger, 1997](#)) will be used to estimate denominator degrees of freedom. The analysis will be performed based on post-DB baseline scores using only the OC without imputation of missing values. Least squares mean and their standard errors based on the MMRM analysis will be plotted by treatment group and visit.

The analysis for change from baseline in YMRS and MADRS total scores by visit will also be performed within modified index episode (manic or depressive).

Sub-domains for PSP are socially useful activities, personal and social relationships, self-care, disturbing and aggressive behaviors.

11.0 SAFETY ANALYSES

The safety analyses will be performed for the OL safety, OL SFU and DB safety Population. The summarization will be overall for the OLTP in the OL safety population and OL SFU period in the OL SFU population, and by treatment group for the DB period and the DB SFU period in the DB safety population. The summarization for the OLTP will use the OL safety population as the denominator. The summarization for the DBTP will use the DB safety population as the denominator. The summarization for the OL SFU period or DB SFU period will use the OL SFU Safety Population or the DB safety population as the denominator respectively.

Safety parameters will include adverse events (AEs), clinical laboratory parameters, vital signs, Electrocardiogram (ECG) parameters, ophthalmology parameters, Columbia–Suicide Severity Rating Scale (C-SSRS), EPS scales, including Abnormal Involuntary Movement Scale (AIMS), Barnes Akathisia Rating Scale (BARS), and Simpson-Angus Scale (SAS), and prolactin level.

For each safety parameter, the last assessment made before the first dose of OL IP will be used as the baseline for all analyses of that safety parameter, unless stated otherwise. Continuous variables will be summarized by number of patients and mean, SD, median, minimum, and maximum values. Categorical variables will be summarized by number and percentage of patients.

The derived visits in the DBTP will use the same strategy as described in Section 10.0. The detailed week mapping windows is provided in Section 16.1.

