7.3.4 Safety Analyses

The safety analyses will be performed for the OL safety, OL SFU, and DB safety populations. The summarization will be overall for the OL period and the OL SFU period, and by treatment group for the DB period and the DB SFU period. The summarization for the OL treatment period will use the OL safety population as the denominator. The summarization for the OL SFU period will use the OL SFU population as the denominator. The summarization for the DB SFU period will use the DB safety population as the denominator.

Safety parameters will include AEs, clinical laboratory parameters, vital signs, ECG parameters, C-SSRS, EPS scales (AIMS, BARS, and SAS), and prolactin level.

For each safety parameter, the last assessment made before the first dose of OL IP will be used as the baseline for all analyses of that safety parameter, unless stated otherwise.

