5.0 OBJECTIVES

- 1) To evaluate the efficacy and safety of cariprazine at a target dose of 3.0 mg/d compared with placebo in prevention of relapse in patients with bipolar I disorder whose current episode (ie, index episode) is manic or depressive, with or without mixed features;
- 2) To evaluate the efficacy and safety of cariprazine at a target dose of 1.5 mg/d compared with placebo in prevention of relapse in patients with bipolar I disorder whose current episode (ie, index episode) is manic or depressive, with or without mixed features, who were initially stabilized on a target dose of 3.0 mg/d.

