10.0 EFFICACY ANALYSES

All efficacy analyses for the OLTP will be performed using the OL ITT Population, unless stated otherwise. Baselines for efficacy parameters in the OLTP will be defined as the last nonmissing efficacy assessment before the first dose of OL IP.

All efficacy analyses for the DBTP will be performed using the DB ITT Population, unless stated otherwise. Baselines for the additional efficacy parameters in the DBTP will be defined as the last nonmissing efficacy assessment before the first dose of DB IP.

All statistical tests will be 2-sided hypothesis tests performed at the 5% level of significance and all confidence intervals (CIs) will be 2-sided 95% CIs, unless stated otherwise.

To accommodate the flexible duration of the OLTP, the derived visits in the DBTP will be named as Week *i* post randomization (or DB Week *i*) for a specific Week *i* after the first dose of the DB study medications. The total exposure to IPs for patients in Week *i* post randomization will vary because of the flexible OLTP. The detailed week-mapping windows is provided in Section 16.1.

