Clinical laboratory test values will be considered potentially clinically significant (PCS) if they meet either the lower-limit or higher-limit PCS criteria listed in [Table 11.2-1](#). The number and percentage of patients who have PCS postbaseline clinical laboratory values will be tabulated overall for the OLTP, and by treatment group for the DBTP. The percentages will be calculated relative to the number of patients with available non-PCS baseline values and at least 1 postbaseline assessment for the corresponding treatment periods (OLTP or DBTP). The numerator will be the total number of patients with available non-PCS baseline values and at least 1 PCS postbaseline value for the corresponding treatment periods (OLTP or DBTP). A supportive tabular display of patients with PCS postbaseline values will be provided, including the PID number, study center number, and baseline and all postbaseline (including non-PCS) values.

In addition, a tabular display showing all AEs that occurred in patients who had PCS postbaseline clinical laboratory values will be provided.

Potential Hy's Law criteria within a 24-hour window is defined by a post baseline elevation of alanine aminotransferase (ALT) or aspartate aminotransferase (AST) $\geq 3x$ ULN, along with total bilirubin (TBL) $\geq 2x$ ULN and a non-elevated alkaline phosphatase (ALP) $< 2x$ ULN, all based on blood draws collected within a 24-hour period.

Patients who meet the potential Hy's Law criteria during the OLTP will be summarized for the OL Safety Population. Patients who meet the potential Hy's Law criteria from the first dose of DB IP to within 30 days after the last dose of DB IP will be summarized for the DB Safety Population. Supportive tabular displays will also be provided.

[figure not shown]

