11.5.3 Extrapyramidal Symptom Scales

A patient will be considered to have treatment-emergent parkinsonism if the patient's SAS score was ≤ 3 at baseline and > 3 at any postbaseline assessment. A patient will be considered to have treatment-emergent akathisia if the patient's BARS score was ≤ 2 at baseline and > 2 at any postbaseline assessment. The number and percentage of patients with treatment-emergent parkinsonism or akathisia will be tabulated overall for the OLTP and by treatment group for the DBTP. Listings of patients with treatment-emergent parkinsonism or akathisia will be provided, including the PID number, baseline and postbaseline values. Listings of all AEs for patients with treatment-emergent parkinsonism or akathisia will also be provided.

Cariprazine
RGH-MD-25 – Statistical Analysis Plan
Amendment #3 – 23 November 2022

Descriptive statistics (n, mean, standard deviation, median, minimum and maximum) for the total scores and the changes from baseline values at every assessment timepoint for each EPS scale (AIMS, BARS, and SAS) will be presented overall for the OLTP and by treatment group for the DBTP.

12.0 HEALTH OUTCOMES ANALYSES**Work Productivity and Activity Impairment Questionnaire Bipolar Disorder
(WPAI-BD)**

The Health Outcome endpoint is change from baseline in percent work time missed, percent impairment while working, percent overall impairment, and percent activity impairment due to bipolar disorder at Week 16 for OLTP, and at Double-blind Weeks 8 and 39 for DBTP, as assessed by the WPAI-BD.

Descriptive statistics (n, mean, standard deviation, median, Q1, Q3, minimum and maximum) will be provided by visit for the OL ITT population and the DB ITT populations.

Baseline for this HEOR endpoint during the DB treatment period for the DB ITT population will be defined as the last nonmissing efficacy assessment before the first dose of DB IP.

The change from baseline will be analyzed during the DB treatment period for the DB ITT population, by using an MMRM with treatment group, region (US and non-US), modified index episode strata (manic or depressive), visit, and treatment group-by-visit interaction as fixed effects, and the baseline value and baseline-by-visit interaction as the covariates. An unstructured covariance matrix will be used. The analysis will be performed based on post-DB baseline using only the OC without imputation of missing values.

WPAI:BIPOLAR DISORDER Related Endpoints Derivation

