16.3 REPEATED OR UNSCHEDULED ASSESSMENTS OF SAFETY PARAMETERS

If a patient has repeated assessments before the start of OLTP, the results from the final nonmissing assessment made before the start of the OL IP will be used as baseline. If end-of-study assessments are repeated or if unscheduled visits occur, the last nonmissing postbaseline assessment will be used as the end-of-study assessment for generating summary statistics. However, all postbaseline assessments will be used for PCS value determinations, and all assessments will be presented in the data listings.

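### The categorical double-blind safety tables measure change from the pre-open-label value, so open-label findings that persist are counted under the randomised arm, placebo included; versions with a double-blind baseline should be added

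*SAP*

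**What the plan says.** SAP 11.0 sets one baseline for safety: "the last assessment made before the first dose of OL IP will be used as the baseline for all analyses of that safety parameter". The sentence carries a qualifier, "baseline for all analyses of that safety parameter, unless stated otherwise". Protocol 7.3.4 has the same rule ("the last assessment made before the first dose of OL IP will be used as the baseline"), and SAP 16.3 repeats it for repeated assessments: "the results from the final nonmissing assessment made before the start of the OL IP will be used as baseline".

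The double-blind tables then refer to baseline without redefining it. The laboratory PCS numerator in SAP 11.2 requires a non-PCS baseline and "at least 1 PCS postbaseline value for the corresponding treatment periods (OLTP or DBTP"). SAP 11.3 flags a weight change of 7% or more from baseline with no observed-value condition. SAP 11.5.3 calls akathisia treatment-emergent "if the patient's BARS score was ≤ 2 at baseline and > 2 at any postbaseline assessment", and the parkinsonism rule has the same form.

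Elsewhere the SAP names a double-blind baseline where it wants one. For double-blind efficacy, SAP 10.0 uses "the last nonmissing efficacy assessment before the first dose of DB IP", and SAP 12.0 does the same for WPAI-BD.

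**The concern.** The first objective is "To evaluate the efficacy and safety of cariprazine at a target dose of 3.0 mg/d compared with placebo" in preventing relapse, and the second asks the same of 1.5 mg/d. The double-blind period is the only randomised comparison that can answer the safety part. Patients reach it after open-label cariprazine, with randomisation possible from Week 12 and open-label treatment lasting up to Week 16 (Protocol section 3).

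A patient who was normal before open-label treatment, became abnormal during it, and is still abnormal after randomisation meets the double-blind criterion whichever arm is assigned. A reader of a by-arm table would take the placebo percentage as what happens on placebo, when part of it arose before randomisation. The table counts do not show how large that part is.

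**Working it through.** **Which tables depend on the rule.** The plan gives no figure to reproduce, so the first step is to go through SAP 11.1 to 11.5.3.

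- Dependent on the pre-open-label baseline: PCS laboratory values, vital signs, weight and ECG; glucose and lipid changes; hypertension shifts; the ECG interpretation shift; QTc increases; treatment-emergent parkinsonism and akathisia; and all mean changes.
- Not dependent: adverse events, serious adverse events and discontinuations (onset date and period; a worsened event gets a new record), C-SSRS counts, orthostatic hypotension (a within-visit difference), and potential Hy's Law cases (absolute multiples of the upper limit of normal).

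**How soon findings are re-measured** (Protocol Table 1; randomisation at Visit 12, Week 16). Weight and vital signs: Visit 13, two weeks later. SAS and BARS: Visit 14, four weeks. Laboratory tests: Visit 18, twelve weeks. ECG: Visit 31/ET only. Early-termination visits can bring laboratory tests and ECG forward. Carry-over is thus most plausible for weight and the movement scales, and less so for laboratory tests and ECG.

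**Categorical tables.** Let q be the share newly abnormal in open-label treatment, f the share of those still abnormal at a double-blind assessment, and p the rate of new double-blind findings. The rate shown is

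q·f + (1 − q·f)·p.

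All rates below are assumptions. Take p = 5% on placebo and 12% on cariprazine: with a double-blind baseline the ratio is 2.40 and the difference 7.0 points. With the planned baseline:

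| q | f placebo / drug | Placebo | Drug | Ratio | Difference (points) |
|---|---|---|---|---|---|
| 5% | 1 / 1 | 9.75% | 16.4% | 1.68 | 6.65 |
| 10% | 1 / 1 | 14.5% | 20.8% | 1.43 | 6.3 |
| 20% | 1 / 1 | 24.0% | 29.6% | 1.23 | 5.6 |
| 30% | 1 / 1 | 33.5% | 38.4% | 1.15 | 4.9 |
| 10% | 0.5 / 1 | 9.75% | 20.8% | 2.13 | 11.05 |
| 10% | 0.2 / 1 | 6.9% | 20.8% | 3.01 | 13.9 |

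For example, the second row is 0.10 + 0.90 × 0.05 = 0.145 and 0.10 + 0.90 × 0.12 = 0.208. With equal persistence the difference is simply (1 − q·f) times the true one, so it shrinks slowly while the ratio falls quickly.

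Rarer findings behave the same way. Take p = 2% and 6% (ratio 3.0, difference 4.0). Equal carry-over of 5%, 10% and 15% gives 6.9% and 10.7%, 11.8% and 15.4%, and 16.7% and 20.1%. The ratios are 1.55, 1.31 and 1.20, and the differences 3.8, 3.6 and 3.4 points.

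**Mean change.** Write the change from the pre-open-label value as the double-blind change plus the open-label change. Randomisation gives the second term the same expectation in every arm, so it cancels. A simulated weight-like variable was used to check this: mean 80, SD 15; open-label gain 2, SD 4; double-blind change +1 on drug and −1 on placebo, SD 4. The between-arm difference was 2.01 with either baseline. The SD of change was 5.75 from the pre-open-label value and 4.13 from the double-blind one.

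In the same simulation, gains of 7% or more were 21.2% on placebo and 32.7% on drug from the pre-open-label value (ratio 1.54, difference 11.5 points). From the double-blind value they were 5.2% and 12.6% (ratio about 2.4, difference 7.4 points). The ratio fell and the difference rose.

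**The case against.** A reader might infer that every by-arm safety table is affected and that the randomised safety comparison as a whole is diluted. The documents do not support that. The main randomised safety evidence, the adverse-event tables, goes by onset date, so akathisia that began open-label and did not worsen is not a new double-blind event. Dilution describes the risk ratio under equal persistence only. The difference moves little in that case and grows if findings resolve on placebo. Nor can carried-over changes be called drug-caused, since the open-label phase has no control.

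The pre-treatment value is also the only unmedicated reference, and protocol and SAP specify it consistently. A double-blind baseline has faults of its own. Weight up 6% open-label and then 3% double-blind is up 9.2% in all (1.06 × 1.03 = 1.092), yet would not meet the 7% rule. A patient up 8% at randomisation who returns to the starting weight on placebo would be flagged for a 7.4% decrease (1 − 1/1.08). This stands, and it is why the planned tables should not be replaced.

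The literal reading of the SAS and BARS rule, under which akathisia that resolved before randomisation would still count, is open but strained. The same paragraph tabulates the open-label and double-blind periods separately, which suggests period-specific assessments. It needs a clarifying phrase.

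Safety is descriptive (Protocol Summary), so no error rate is at stake. Listings of baseline and postbaseline values for flagged patients allow carry-over to be traced patient by patient, though not from the summary counts.

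**Conclusion.** The point holds for the categorical double-blind tables named above. Under the plan as written, persistent open-label changes count under the randomised arm, placebo included, and the counts mix them with new findings. The clearest cases are weight change of 7% or more and the SAS and BARS tables.

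The size cannot be fixed from the documents. For assumed new rates of 5% and 12% and equally persistent carry-over of 5% to 30%, the placebo figure rises to between 9.75% and 33.5% and the ratio falls from 2.40 to between 1.68 and 1.15. The difference falls only from 7.0 to between 6.65 and 4.9 points. With unequal persistence the difference can exceed its true value. Mean-change contrasts are unbiased but less precise.

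One limit remains: the ophthalmology section is redacted, and the PCS laboratory, glucose, lipid and visit-window tables are not shown, so an exception stated there cannot be ruled out.

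**What to change.** Keep the planned tables and label them as cumulative change from before open-label treatment. Add to SAP 11.2 to 11.5.3 a second version of each affected categorical double-blind table, with the last value before the first dose of double-blind product as baseline and only double-blind assessments counted. State in SAP 11.5.3 that the double-blind SAS and BARS counts use double-blind assessments only.

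No new data are needed: Visit 12 already collects laboratory tests, vital signs, weight, ECG and the movement scales (Protocol 8.4.4). The cost is SAP wording and one extra set of tables, so this is a cheap improvement. The added tables have an on-drug baseline. They therefore miss cumulative change and may flag a return towards the pre-treatment value on placebo, and a footnote should say so.

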11.1 ADVERSE EVENTS

Aes will be coded by system organ class and preferred term using the *Medical Dictionary for Regulatory Activities* (MedDRA), Version 21.0 or newer.

An AE will be considered a treatment-emergent adverse event (TEAE) if the AE began or worsened (increased in severity or became serious) on or after the date of the first dose of OL IP. Per eCRF instructions, a new AE record will be created with a new AE onset date for any AE that worsens. Therefore, TEAEs can simply be identified as those Aes with recorded onset date (and time, if known) on or after the date of the first dose of IP.

The number and percentage of patients reporting TEAEs during the OLTP will be tabulated by system organ class and preferred term; by system organ class, preferred term, and severity; and by system organ class, preferred term, and relationship to IP.

The number and percentage of patients reporting TEAEs during the DBTP will be tabulated for each treatment group by system organ class and preferred term; by system organ class, preferred term, and severity; and by system organ class, preferred term, and relationship to IP. The total number and percentage of TEAEs during the DBTP will also be summarized by severity and relationship to IP for each treatment group.

The number and percentage of patients reporting TEAEs during the OL SFU period will be tabulated by system organ class and preferred term for the OL Safety Population. The number and percentage of patients reporting TEAEs during the DB SFU period will be tabulated by system organ class, preferred term, and DB treatment group for the DB Safety Population.

For OLTP, DBTP, or SFU period, if more than 1 AE was coded to the same preferred term for the same patient, the patient will be counted only once for that preferred term using the most severe and most related occurrence for the summarization by severity and by relationship to IP.

An AE that occurs more than 30 days after the date of the last dose of DB IP or occurs after the last SFU visit (whichever comes last) will not be summarized except for Aes related to reported pregnancies. Aes associated with pregnancies reported in the protocol-required timeframe up to approximately 12 weeks following the last dose of DB IP will be summarized.

The number and percentage of patients with common ($\geq 2\%$ of patients in any treatment group) TEAEs will be summarized by preferred term for OLTP and be summarized by preferred term and treatment group for DBTP.

The number and percentage of TEAEs leading to premature discontinuation of IP during the OLTP will be summarized by preferred term. The incidence of Aes leading to premature discontinuation of IP during the DBTP will be summarized by preferred term and treatment group.

An AE will be considered a treatment-emergent serious adverse event (TESAE) if it is a TEAE that additionally meets any serious adverse event (SAE) criterion.

Summary tables will be provided for patients with TESAEs if these occurred in 5 or more patients. The number and percentage of patients with TESAEs will be summarized for OLTP, DBTP, and SFU period.

For the Screened Population, listings will be presented for patients with SAEs, patients with Aes leading to premature discontinuation, and patients who die (if any). All patients with SAEs, including SAEs reported during the screening period and the SFU period, and patients discontinuing because of Aes occurring before the start of OLTP will be included in these listings.

The number and percentage of patients with EPS TEAEs, EPS SAEs, and EPS Aes leading to premature discontinuation of IP will be summarized overall for the OLTP in the OL safety population and by treatment for the DBTP in the DB safety population separately.

The number and percentage of patients reporting TEAEs of ocular events of special interest will be summarized overall for the OLTP in the OL safety population and OL SFU period in the OL SFU population, by treatment for the DBTP and DB SFU in the DB safety population. A listing of all reported ocular events of special interest will be provided.

